Patients presenting with, or developing during the study period, severe actue renal failure requiring renal support, will receive continuous renal replacement therapy (CRRT) as per standard local practices. This would apply to subjects in both SOC and DIALIVE arms. For those in the DIALIVE arm, the same vascular catheter which is used for DIALIVE treatment may be used for CRRT following the completion of the DIALIVE treatment session. It is however envisaged

that increased intensity of dialysis component in the DIALIVE system (from 1lit/hr to 1.5lit/hr) and allowance for fluid removal in the new protocol may delay or remove altogether the need for CRRTin these situations. The decision for additional CRRT would depend on clinical situation and will be taken by the site PI.

DIALIVE arm consists of standard of care (defined above), plus DIALIVE treatment.

A DIALIVE treatment session denotes treatment for the day, whereas A DIALIVE treatment cycle refers to the total number of treatment days.

A DIALIVE treatment **session** = A minimum, cumulative duration of 8 to 10 hrs (± 30 min) of the DIALIVE treatment, thus allowing for breaks which may be planned (for example patients needing to go for imaging) or unplanned (device clotting, issues with vascular access or other any other unplanned reasons). A break within a treatment session (consisting of a cumulative time longer than 4hrs), or a cumulative duration of less than 8 hrs of dialysis during one day constitutes a session failure for that day. A session failure will require to restart the dialysis session within 24 hrs after the end of the previous session and will reset the start of the dialysis cycle.

A DIALIVE treatment **cycle**= Consists of 3 consecutive days of 8-10 hrs of DIALIVE treatment sessions on each day within the 10 day window period. A break of more than 24hrs between each treatment session will require a new baseline (i.e. a new treatment cycle commenced). A second failed treatment session within the 10 day window period would result in patient exlusion. The patient must have completed one successful treatment cycle within the 10 day window period to be considered evaluable.

Day of randomization constitutes study Day 0.

The first treatment session (DIALIVE arm only) must commence before the end of study Day 1. As such, dialysis might also start on the day of randomization which might created confusion as 'the first day of dialysis' then concurs with DAY 0 of the study schedule.

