4.2 Hypotheses and claims

The underlying hypothesis is that DIALIVE will significantly improve the prognosis of patients with ACLF by i) exchanging irreversibly damaged native albumin, which accumulates during this disease process and is ineffective in its function, with fresh albumin, and ii) removal of endotoxins, inflammation and endotoxaemia being the central pathogenetic feature of this illness.

This is a first into man study of a novel Liver Dialysis Device. No specific hypothesis is to be statistically assessed in this first feasibility study. Randomization of patients is implemented to obtain unbiased clinical data appropriately balanced between SoC and DIALIVE treated patients to provide fundamental learning data on the outcome of treatment in both study arms, in line with the recommendations of the DSMB (see appendix 7). To this end, safety data, are regularly reviewed (i.e. after each cohort of patient enrollment) but also other clinical parameters are reviewed, to learn and adjust study design when necessary and as appropriate.

Based on this perspective it is the goal to obtain an adequate number of observations in each study arm, with emphasis on the learning from DIALIVE treatment. Future trials will be defined to assess the efficacy of DIALIVE treatment to the appropriate extend.

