5.1.6. Equipment to be used for assessing the clinical investigation

All equipment except for the DIALIVE device, the EAA luminometer for endotoxin analysis, and the Primsmaflex platform¹¹ will be the property of the Investigator(s) and/or institutions and maintained and calibrated according to institutional guidelines. Records of maintenance and calibration will be made available at the Sponsor's request.

5.1.7. Replacement of subjects.

30 evaluable patients will be recruited across all sites to receive either treatment using the DIALIVE or SOC. Screen failures will be replaced to achieve an even balance in each cohort. The patient numbers will be increased and replaced if there are dropouts during the treatment period to allow 30 evaluable patients to be included. Dropouts can be i) patients who withdraw their consent, ii) patients who are considered 'not evaluable' because of an incomplete dialysis cycle (for DIALIVE patients) or iii) if a patient dies in the 10-day period following randomization to the SOC-arm, or iv) patients who are excluded based on a stopping rule.

A dropout rate of 17% is anticipated on the basis of observations made during execution of this study in the first 2 cohorts of patients. Patients who drop-out for reasons of an incomplete dialysis cycle are followed up for a duration of 28 days post-randomization.

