5.2. Investigational device exposure

For the randomization an Interactive Wireless Randomization System (IWRS) is used, which is linked to the study data base. Randomization is automatically assigned through the IWRS system. Patients are randomised to either the DIALIVE or SOC arm in a 1:1 ratio.

¹¹ The prismaflex platform will be provided by Yaqrit to those sites that do not have access to such haemofiltration machines. The machine will remain the property of Yaqrit Ltd during and after the study. A mainenance agreement in such circumstances will be established with each institution.

Patients will be assigned into five (5) Cohorts. Each cohort will consist of six (6) patients (3 DIALIVE: 3 SOC). If there are dropouts in any of the following cohorts during the study period, patients will be replaced in each of the cohorts described below to reach the appropriate number of 6 evaluable patients in each cohort.

Cohort 1: including 3 control and 3 DIALIVE treated patients. Cohort 2: including 3 control and 3 DIALIVE treated patients. Cohort 3: including 3 control and 3 DIALIVE treated patients. Cohort 4: including 3 control and 3 DIALIVE treated patients. Cohort 5: including 3 control and 3 DIALIVE treated patients.

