6. STATISTICAL CONSIDERATIONS

An independent statistician will be responsible for all statistical aspects of the investigation.

All statistical analyses will be carried out on the safety population, defined as the subset of randomised patients who receive at least one treatment. No imputation of missing values will be implemented. Only available data will be analysed. In addition, a sensitivity analysis will be carried out to check the main safety results using SAE-data of all evaluable patients, defined as all those patients who received standard of care or those who received the correct dialysis treatment cycle.

Due to the nature of the study all statistical analyses will be descriptive. The categorical variables will be summarised by means of the count and percentages corresponding to each variable category, while continuous variable will be summarised by the mean and Standard Deviation of each distribution or the median and min-max values in case of those variables non-normally distributed.

Clinical Investigation Plan CIP YAQ-002 Version: 7.0 10 October 20	19
--	----

For each treatment arm, treatment-emergent AEs, SAEs, SADEs, ADEs, USADEs and DDs will be summarised by organ system and treatment causality. The number and percentage of patients discontinuing the study due to AEs, SAEs, SADEs or other stopping criteria confirmed by the DSMB (withdrawal of patient consent; development of septic shock; progression to ACLF Grade 3b or more; disseminated Intravascular coagulation; unanticipated serious adverse device effects, device deficiencies, or in the opinion of the PI, the treatment is unsafe to continue) will be summarised by treatment arm.

Secondary and exploratory parameters (changes from baseline at each study visit) will be descriptively analysed by treatment arm by means of the appropriate statistics.

Statistical analyses of safety data will be run when each study cohort is completed (minimally one week FU) and the corresponding results will be communicated to the DSMB.

Special interim data extraction required to comply with the EU ALIVER program.

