B) upon review of the safety aspects observed in cohort 2 of the study.

[figure not shown]
14 subjects have been enrolled to the study so far; 8 DIALIVE and 6 SOC, 2 of 8 DIALIVE patients were non-evaluable as per the study protocol since they failed to complete the minimum treatment required for analysis. Overall, with the exception of the 2 non-evaluable DIALIVE patients, the intervention seems to be safe and is well tolerated with some expected adverse events such as a degree of hypotension, mild platelet consumption and potential complications related to the lines being used to deliver the treatment. The two deaths in the DIALIVE arm, both occurring within 24-36 hours of treatment having been commenced, appear to be multifactorial including progression of the disease itself and the learning curve of the sites using such treatment for the first time thus sometime not realising the nuances of such treatment. Following the recommendations made at the interim DSMB meeting whereby a standard document was created to capture these nuances for ready reference to the site teams, the three DIALIVE patients treated since then had a very stable treatment course.

We therefore, based on the evidence provided to us by the central study team and the sponsor, feel reasonably confident that the study should continue to the next cohort as and when practical.

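### The scheduled DSMB safety analysis waits for patients who completed the DIALIVE cycle, so a DIALIVE patient lost early does not advance the review and another is exposed first

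*Protocol*

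**What the plan says.** Four rules in the Protocol combine.

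- **When the analysis runs.** Section 6: "Statistical analyses of safety data will be run when each study cohort is completed", with at least one week of follow-up, and the results go to the DSMB. The Synopsis gives the same trigger, and section 4.2 also has safety data reviewed cohort by cohort.
- **When a cohort is full.** Section 5.2 sets five cohorts of 3 DIALIVE and 3 SOC patients. After dropouts, "patients will be replaced in each of the cohorts described below to reach the appropriate number of 6 evaluable patients in each cohort".
- **Who counts on DIALIVE.** Section 2.2: "The patient must have completed one successful treatment cycle within the 10 day window period to be considered evaluable". A cycle is three consecutive days of sessions.
- **Who is replaced.** Section 5.1.7 lists consent withdrawals, DIALIVE patients with an incomplete cycle, SOC patients who die within 10 days, and "patients who are excluded based on a stopping rule". It states no limit on replacements and anticipates 17% dropout.

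Appendix 7 B records the position at the cohort 2 review: "14 subjects have been enrolled to the study so far; 8 DIALIVE and 6 SOC". Two of the 8 DIALIVE patients were not evaluable. It also reports two DIALIVE deaths, both within 24-36 hours of starting treatment.

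**The concern.** The cohort review exists so that the DSMB can look at accumulated harm before more patients are treated. Section 5.3.7 gives this as a reason for the small sample: it limits the number put at risk and lets the DSMB decide on continuation cohort by cohort.

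Under the rules above, progress towards each scheduled review is measured by DIALIVE patients who got through three sessions. A patient who dies on the first or second day contributes nothing to that count. The place is refilled and a further patient is exposed before the scheduled analysis falls due. The schedule therefore slips most when early losses on the device are most frequent. This is a first-in-man study that section 5.5 rates as high risk, with safety as its primary endpoint.

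**Working it through.** **Reproducing the Protocol's own figure.** Section 5.1.7 derives 17% from the first two cohorts. With the Appendix 7 B counts:

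- 2 non-evaluable / 12 evaluable = 16.7%, which rounds to 17%.
- 2 / 14 enrolled = 14.3%.
- 2 / 8 DIALIVE = 25%.

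The stated figure thus matches losses divided by evaluable patients over both arms. Both non-evaluable patients were on DIALIVE, so that arm's observed rate is 25%. Both rates are carried forward.

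**Does the record fit the rule?** Two full cohorts need 6 evaluable DIALIVE and 6 SOC patients. Adding the 2 non-evaluable DIALIVE patients gives 8 and 6, which is 14 in all, exactly the enrolment reported. So 8 patients had been allocated to DIALIVE by the second review, against a nominal 6. Appendix 7 does not say outright that the two who died are the two non-evaluable patients. However, a patient who dies within 36 hours could hardly have completed sessions on three consecutive days.

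**Exposures up to one scheduled trigger.** Let d be the probability that a treated DIALIVE patient does not become evaluable, and N the number treated until the third evaluable one. With independent patients and constant d, N is negative binomial:

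- E(N) = 3 / (1 − d)
- P(N ≥ 4) = 1 − (1 − d)³
- P(N ≥ 5) = 1 − (1 − d)³ − 3d(1 − d)³

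| | d = 0.17 | d = 0.25 |
|---|---|---|
| (1 − d)³ | 0.572 | 0.422 |
| Expected exposures (nominal 3) | 3 / 0.83 = 3.6 | 3 / 0.75 = 4.0 |
| At least one extra exposure | 43% | 58% |
| At least two extra exposures | 14% | 26% |
| Expected over five cohorts (nominal 15) | 18.1 | 20.0 |

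These counts run to the point where the third evaluable DIALIVE patient is reached. They exclude anyone treated during the follow-up week and any further delay from filling the SOC places.

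**Delay.** Section 5.3.8 gives 39 months of recruitment for 30 patients, or 39 / 30 = 1.3 months per patient. With even accrual and the next patient assigned to DIALIVE, each replacement postpones the scheduled review by about that much.

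**The case against.** **Safety oversight does not rest on the cohort analysis alone.** Under section 14, once unacceptable risk is suspected the sponsor must suspend the study and send all information to the DSMB. Sections 12.2 and 12.4.1 require every death to be reported as an SAE within 3 calendar days. Appendix 6 requires three-monthly SAE summaries in the UK and quarterly ones in Germany, whatever the state of the cohorts. Section 3.5 promises regular safety review by the TMG and DSMB. Section 12.3.3 refers to review times in a DSMB charter that is not at hand. Appendix 7 B shows that an interim DSMB meeting took place before the cohort 2 review. The DSMB judged the two deaths to appear multifactorial, and the three DIALIVE patients treated after its interim recommendations had a stable course. All of this stands. It rules out the inference, which a reader might draw, that the DSMB would not learn of early deaths until a cohort fills. But the national summaries go to authorities, the suspension clause depends on someone forming a suspicion, and none of these provisions is tied to the number exposed.

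**Not every safety stop has this effect.** Section 5.3.3 allows restart after some stops, and section 2.2 allows a new cycle within the 10-day window. Nor is d a toxicity rate: clotting, vascular access problems and consent withdrawal can also leave a cycle incomplete. The point is therefore confined to losses that prevent completion of the cycle.

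**No early event is lost.** The safety population in section 6 includes anyone who received at least one treatment, of any duration. That is correct, and the point concerns timing and added exposure only.

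**A cohort could be read as six enrolled patients.** Section 4.2 and Appendix 7 A speak of enrolment. Section 5.2 nevertheless fixes the cohort at six evaluable patients, and the 14 enrolled at the second review fit that reading.

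**Conclusion.** The point stands in limited form. As written, the scheduled DSMB safety analysis is triggered by completed DIALIVE cycles, and no trigger in this Protocol counts exposed patients. The expected excess is 0.6 to 1.0 DIALIVE patient per scheduled review, with a 43% to 58% chance of at least one extra exposure.

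This assumes independent patients, a constant loss rate of 17% to 25%, replacement within the same arm, and no exposure-based trigger in the charter. The 25% rests on only 8 patients. The 17% is a figure for both arms, applied here to DIALIVE.

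It is tempting to go further and say that a badly tolerated device would double the exposure before each review. At a 50% loss rate the formula does give 6.0, but nothing in the documents supports such a rate, and the provisions for unscheduled review would probably intervene. Higher rates are illustrative only. Later cohorts admit grade 3a patients, so the rate may change, but the Protocol gives no figure for early loss in that group.

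**What to change.** In sections 4.2 and 6, with the Synopsis brought into line, state that the cohort safety analysis is run at the earlier of two points:

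1. The cohort's planned number of DIALIVE patients (3) have had any exposure, evaluable or not, and each has completed the Protocol's minimum one-week follow-up or has died or withdrawn earlier.
2. The cohort is complete.

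The clause on earlier death or withdrawal is essential. Without it, a patient who died on the second day would never meet the follow-up condition, and the same gap would return. The analysis should include every exposed patient and every replaced patient in both arms. The DSMB charter should carry the same trigger; if it already has an exposure-based one, sections 4.2 and 6 need only be aligned with it.

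This changes no treatment or patient-level rule, and replacement to reach 30 evaluable patients can continue. The cost is a protocol amendment, which section 8 makes subject to ethical and regulatory approval before use, in several countries. There may also be a few extra DSMB calls when DIALIVE patients are lost early.

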7. DATA MANAGEMENT

7.1.1. Procedures for data review, database cleaning, and issuing and resolving data gueries.

All clinical investigators will have current Good Clinical Practice (GCP) training, specifically ISO 14155 standards for conducting a clinical Investigation.

Responsibilities

Clinical Investigation Plan	CIP YAQ-002	Version: 7.0 10 October 2019
-----------------------------	-------------	------------------------------

Data Management will be the responsibility of the Sponsor/designee. All documents and data shall be produced and maintained in a way that assures control and traceability. All documents, and subsequent versions, related to a clinical investigation shall be identifiable, traceable and appropriately stored to provide a complete history of the clinical investigation. Only authorised individuals will have access to the electronic system after appropriate training has been provided.

Data Collection

All collected patient data will be treated confidentially and identified only by a unique patient identification number. Medical records relating to clinical investigation, including those that are electronically maintained and those that may contain information that would identify an individual patient will remain confidential, but may be reviewed by, released, and/or transmitted to representatives of the hospital, regulatory authorities, or its agents when reasonable and appropriate for the conduct of the study.

An electronic Case Report Form (eCRF) will be used in the study and completed for every patient who is enrolled for participation. The eCRF will be developed and held by the data management centre of European Foundation for Chronic liver Failure (EF-CLIF), Barcelona, Spain. Data entered in the eCRF must be consistent with the source documents (medical and nursing notes, laboratory reports, ECGs, echocardiogram). Data must be entered by the site in a timely manner and be consistent with the source. The PI (or designee) will be responsible for the ensuring the eCRFs are signed. Any changes to the initial data recorded must be signed for to ensure an appropriate audit trail is maintained. The Trial Monitor(s) will carry out on-site monitoring during the study and at the end of the study to ensure accuracy and quality of data (Source Data Verification). Site investigators will ensure the Monitor's access to patients' medical records, laboratory reports, imaging reports, and other patients' records needed. Site Investigators will cooperate with the Trial Monitor to ensure that any problems detected in the course of these monitoring activities are resolved.

Avoidance of confusion.

The procol allows for a start of DIALIVE dialysis on the day of randomization (DAY 0). As this constitutes the first day of treatment in the DIALIVE-arm, it might be confused with "DAY 1" of the study scheme. The currently available electronic data base (eCRF) also does not provide data entry options for "DAY 0" data collection, other than directly related to the randomization assignment. If dialysis is performed on DAY 0, then clinical data are required to be entered on the eCRF indicated as "DAY 1". The date of treatment will allow, however, to retrospectively reconstruct the exact timing of dialysis sessions and to identify the 'eligible dialysis cycle' to be considered for the end-point analysis.

7.1.2. Procedures for verification, validation and securing of electronic clinical data systems

The study database will be located at the above data management centre. The database will be aligned with the case report forms so that the data captured are complete, accurate, reliable and consistent. Database design will be documented at each stage of development, including (but not limited to) test runs, training exercises, security checks, periodic reviews to confirm data integrity and compliance with operational specification. Once completed, the system will be validated to ensure that it is fit for purpose for the trial.

Appropriate software will be used in developing/designing a database to ensure:

- Ease of use with appropriately controlled access
- Prevention of duplicate entries
- Field validations, where appropriate

Clinical Investigation Plan CIP YAQ-002 Version: 7.) 10 October 2019
---	-------------------

- Consistent data coding (e.g. MedDRA coding or other convention which is developed at the start of the study)
- Consistent and accurate downloads for analyses
- Full audit trail possible of data entered and any changes made.
- Regular back-ups

Prior to database lock, the entire database will be verified to ensure that there are no outstanding errors or unjustified missing data. When all queries have been resolved the database will be locked.

Statistical review of the Database

There will be a requirement to ensure that all the trial data have been received, verified, fully coded and cleaned for analysis with all queries resolved before locking the database for analysis. Unlocking of the database will only be undertaken in a strictly controlled environment and rationale for doing so will be fully documented.

The designated statistician will receive the full and dated download of the database with a complete and accurate dataset used for analysis. This will be retained separately from the live database to allow reproducible analyses (database-lock).

A final copy of the database will be provided to the study site. Where data is transferred electronically, this will be in accordance with applicable Data Protection regulations. There will be a documented record of data transfer and measures in place for the recovery of original information after transfer.

